## **Hypotheses of main effects**

**H1a.** We expect a large main effect of treatment on total percentage sick leave from pre- to post treatment, with gains maintained at follow up.

**H1b.** We expect a large main effect of treatment on the number of participants with full return to work from pre- to post treatment, with gains maintained at follow up.

**H2.** We expect a large main effect of treatment on reduction on symptoms of depression and anxiety.

**H3.** We expect a positive main effect of treatment on Return to Work Self-Efficacy, from pre to post treatment, and sustained through follow up.

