## Methods and procedures

### Design

This study is a non-randomized, single arm, multi-center mixed methods clinical trial in a naturalistic setting (see Figure 1 for an overview of the study design). Participants are recruited in a real life setting in Norwegian specialised mental health care. After recruitment participants fill out questionnaires pre, interim and post treatment, in addition to follow up at 6 and 12 months after completing treatment. Interim measures are collected after six weeks. After the treatment intervention, some participants are invited to an in-depth qualitative interview.

[figure not shown]

Figure 1. Study design.

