## Sample

Inclusion criteria for the sample are 1) being an outpatient in specialised mental health care service, 2) above 18 years old, 3) full or graded sick leave, or on work assessment allowance 4) primary diagnosis of F30 – F40 (ICD-10), 5) currently employed.

Exclusion criteria are 1) ongoing psychotic disorder and/or mania, 2) ongoing substance abuse, incl. sedative medications, 3) ongoing episode of major depression, 4) organic brain disease, 5) severe reading and writing difficulties.

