## Measures

**Demographic variables.** Self-reported data will be collected on gender, age, level of education, length and degree of sick leave, length of mental health problems and marital status. Primary and secondary F-diagnosis (ICD-10) will be reported by the eTherapist.

**Questionnaires.** *Primary outcome measures:* The reduction in the degree of sick leave is one of our primary outcomes and will be measured through self-report. The first question is: “are you currently on sick-leave?”. The second question is activated if there is a positive answer to the first: ” To what degree are you currently on sick-leave?”. The answer is given on a 0-100 scale with 5 point increments.

The Return to Work Self-Efficacy Scale (RTWSE-11; (Lagerveld et al. 2010, Gjengedal et al. 2021) is an 11-item questionnaire measuring an individual’s confidence in their ability to work and perform work tasks. Items are scored on a scale from 1 (“Totally disagree”) to 6 (“Totally agree”). Items 2 and 6 are reversed. Total scores of 3.7 or below are associated with less probability of returning to work, while scores of 4.6 and above are associated with increased probability of returning to work (Gjengedal et al. 2021).

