## Statistical analyses

**Quantitative analyses.** In order to identify factors associated with treatment success and outcomes, hierarchical linear mixed modelling analyses (HLM, “multilevel”) will be conducted. In longitudinal HLM, measurement occasions (time) are nested within participants. Fixed effects are average (main) effects, and do not vary across subjects. Random effects vary across subjects and/or measurement occasions (e.g., a random intercept model vs a random intercept, random slope model). In these models, data may be missing at random and at different occasions for different subjects (Tasca & Gallop 2009). The models will be checked if they fulfil the model assumptions of normality of residuals, linearity and homoscedasticity. The dependent variables are sick leave, work related self-efficacy (as measured by RTWSE-11), depression severity (PHQ-9), anxiety (GAD-7), well-being, symptoms, risk and function (CORE-OM) and impairment in functioning (WSAS). The predictors are: Treatment (time), duration of sick-leave prior to treatment, treatment credibility, work related self-efficacy, depression severity and adherence. Comparisons are modelled through main effect and interaction effect analysis (e.g. Time x “Baseline work absenteeism” interaction). Predictors will be centred using grand mean centering. T-values and degrees of freedom will be estimated using “Satterwaite” correction (Luke 2017). The effects sizes will be converted from *t*-values and degrees of freedom to Cohen’s *d* using the R-package “effectsize”. Estimating indirect effects (mediation), we will apply “causal mediation analysis” (CMA), that is a method to split a total effect of an independent predictor (X) into a direct (C) and indirect effect (M). The indirect effect is transmitted through a mediator to the outcome. CMA will be conducted under the assumption of sequential ignorability. The X will be measured at baseline, the M at intermediate treatment, and the outcome(s) at post-treatment (Zhang et al. 2016). See Figure 2 below for a tentative model.

[figure not shown]

Figure 2. Model of mediation.

Corrections for multiple analyses will be done by using Jaccard's correction (Jaccard, 1998) to decrease risk of Type I error when applying several statistical tests.

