## Power analyses

In a multilevel model, the fixed effects are comparable to ordinary repeated t-tests, and thus, using this as a proxy model with a moderate effect size ( $d = 0.6$ ), power = 0.8, alpha = 0.05, tails = "two.sided", we need 25 subjects for detecting a single main effect Murayama, Usami and Sakaki (2022); see [Summary-statistics-based power analysis \(shinyapps.io\)](#). But, as stated by Van Voorhis and Morgan (2007): "*if the circumstances allow, a researcher would have better power to detect a small effect size with approximately 30 participants per variable*" (page 48). Following this rule of thumb, we plan for 30 participants per predictor (unique main effects), thus a total sample size of 300 participants. Calculating a drop-out rate of 30% gives a total sample size of  $N = 390$ . Calculating power for indirect effects – or mediation – we used the following online shiny app [Monte Carlo Power Analysis for Indirect Effects \(shinyapps.io\)](#), published by Schoemann, Boulton and Short (2023). Using (El Alaoui et al. 2015) as a proxy study for the direction and strength of association between our variables, they found that both treatment credibility and treatment adherence were significantly predictors of faster change and lower post treatment scores in a routine psychiatric care based ICBT for social anxiety disorder. In the same study, a high level of treatment credibility was associated with higher treatment adherence. Hence, defining X = treatment credibility, M = treatment adherence and Y = treatment outcomes, we set the correlation of X-M (a-path) = 0.3 ( $SD = 1$ ), X-Y (c-path) = 0.30 ( $SD = 1$ ) and M-Y (b-path) = 0.30 ( $SD = 1$ ), power = 0.8, alpha = 0.05, setting random seed to "0512", using 5000 replications with 20000 Monte Carlo draws per replication, we need  $N = 155$  to have a power of 0.80, 95% CI [0.79-0.82].

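### Cohen's d converted from mixed-model t and df depends on the within-person correlation and the number of occasions as well as on the change, so it describes the H1a and H2 changes poorly

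*Protocol*

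**What the plan says.** Statistical analyses (Protocol) plans linear mixed models with occasions nested in participants. Treatment enters as time, and t and df come from a Satterthwaite correction. The effect-size rule follows: "The effects sizes will be converted from *t*-values and degrees of freedom to Cohen’s *d", using the R package effectsize. The text does not say which conversion form applies and names no standardising SD. The random-effects structure is mentioned only by example: "a random intercept model vs a random intercept, random slope model".

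Under Design, "participants fill out questionnaires pre, interim and post treatment, in addition to follow up at 6 and 12 months after completing treatment", so up to five occasions can enter a model.

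Two hypotheses of main effects are worded in terms of size. H1a reads "We expect a large main effect of treatment on total percentage sick leave from pre- to post treatment, with gains maintained at follow up". H2 reads "We expect a large main effect of treatment on reduction on symptoms of depression and anxiety". Neither gives a number or a scale. H1b also expects a large effect, but it concerns a count of participants and is outside this point.

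The only numerical d for a main effect is the 0.6 under Power analyses, called moderate. It rests on the statement that "the fixed effects are comparable to ordinary repeated t-tests".

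**The concern.** In a paired t-test, t divided by sqrt(df) is close to the mean change over the SD of the change. In a mixed model with more occasions, that link weakens. Under a random intercept the df for a time contrast grows with the number of occasions, while the t for the same pre-to-post contrast does not. The converted d then falls although nobody has changed less. It also rises with the within-person correlation, which may differ between outcomes.

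This is a single-arm study whose first research question asks how far the program affects return to work, symptoms and functioning, so the size of the change is a main result. If that size is expressed by the converted d, a reader cannot tell whether a value reflects the change or the model. Nor can the value be compared safely across outcomes or with the planning value of 0.6.

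**Working it through.** **Inputs from the Protocol.** Planning d = 0.6, power 0.80, two-sided alpha 0.05, 25 subjects for a single main effect, total N = 390 with 30% drop-out (Power analyses); up to five occasions (Design).

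**Assumptions not in the Protocol.** Compound symmetry with equal SD at each occasion and within-person correlation rho from 0.3 to 0.8; complete data; random intercept with categorical time; paired form t/sqrt(df); an example change of 0.8 baseline SD; N = 390 × 0.70 = 273.

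**Step 1: the Protocol's own figure.** A paired t-test with d = 0.6 and two-sided alpha 0.05 has exact power 0.804 at n = 24 and 0.821 at n = 25. The stated 25 is reproduced within one subject. The planning d therefore behaves as a change-score d (mean change over SD of the change).

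**Step 2: the formula.** Let D be the pre-to-post change in baseline SDs and T the number of occasions in the model.

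- t = D × sqrt(N / (2(1 − rho))), which does not depend on T
- df = (N − 1)(T − 1), that is 272, 544 and 1088 for T = 2, 3 and 5
- converted d = t / sqrt(df), approximately D / sqrt(2(1 − rho)(T − 1))

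Both rho and T remain in the result; N almost cancels. Moving N from 155 to 390 shifts the values below by at most 0.002.

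**Step 3: a change of 0.8 baseline SD.** Example for rho = 0.5: t = 0.8 × sqrt(273 / 1.0) = 13.22. Dividing by sqrt(272) = 16.49, sqrt(544) = 23.32 and sqrt(1088) = 32.98 gives 0.80, 0.57 and 0.40.

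| rho | t | T = 2 | T = 3 | T = 5 |
|---|---|---|---|---|
| 0.3 | 11.17 | 0.68 | 0.48 | 0.34 |
| 0.5 | 13.22 | 0.80 | 0.57 | 0.40 |
| 0.7 | 17.06 | 1.03 | 0.73 | 0.52 |
| 0.8 | 20.90 | 1.27 | 0.90 | 0.63 |

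The change divided by the baseline SD is 0.8 in every cell. If the two-group form 2t/sqrt(df) were used instead, each figure would double.

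**Step 4: the planning scale, where rho drops out.** With a change-score d of 0.6, t = 0.6 × sqrt(273) = 9.91. Dividing by the same three square roots gives 0.60, 0.425 and 0.30 for two, three and five occasions.

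**The case against.** **These details belong in an SAP.** The number of occasions, the random effects and the conversion form can all be fixed there, and the named package may settle the form; that cannot be checked from the text. This stands in part, and openness on these items is not the point here. The Protocol does state the conversion itself. Fixing the model would stop the value moving between analyses, but would not turn it into a measure of change. With two occasions fixed, the same 0.8 SD change still runs from 0.68 to 1.27 with rho. With five under a random intercept, it stays below 0.8 throughout the assumed range.

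**On the simplest reading the Protocol is consistent.** With two occasions and the paired form, 0.6 stays 0.60. That is correct. The fall to 0.425 and 0.30 needs more occasions and a random intercept without a random slope, which the Protocol mentions only as one of two examples. H1a's reference to follow-up makes a longer model natural but does not prescribe it.

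**A random slope changes the df.** It does, but no figures for it are offered. Under compound symmetry the true slope variance is zero. In simulation it would be estimated at zero in about half of data sets with three occasions and at least about 90% with five. Random-slope values on these assumptions would not be what the fitted model returns, and a linear trend over all five occasions is a different estimand from the pre-to-post change.

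**Nothing excludes original units.** True: a linear mixed model yields them directly. The Protocol simply does not name them as the measure of size.

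**Conclusion.** The point holds as a minor matter of reporting and interpretation. For time effects, the stated conversion mixes the change with the within-person correlation and, under a random intercept, with the number of occasions. On the assumptions listed, one and the same 0.8 SD change is reported as anything from 0.34 to 1.27.

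Three stronger readings are not supported:

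- A reader might infer that H1a and H2 will be accepted or rejected on this d. The Protocol ties the word large to no scale or cut-off, and the study seeks preliminary results.
- A reader might infer that effects will be understated. The direction is not fixed: two occasions with rho 0.5 return 0.80 exactly, and higher correlations exceed it.
- A reader might infer that the inference is at risk. Tests, p-values and sample size do not depend on the conversion.

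The correlation range, compound symmetry and complete data are assumptions. The planning-scale result in step 4 needs no value for the correlation, but still needs the random-intercept model and the paired form.

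**What to change.** Replace the conversion sentence in Statistical analyses by:

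> For time effects (pre to post and pre to each follow-up) we report the model-estimated change with 95% CI in original units (percentage points for sick leave, scale points for questionnaires) and, for the questionnaires, that change divided by the observed baseline SD with 95% CI. Descriptions of an effect as large refer to these measures and not to a d converted from t and df. For predictor and interaction effects, d converted from t and df may be given as a secondary descriptor, with the conversion form named.

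A numerical threshold for a large effect, set before the data are seen, would help but is optional.

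The cost is a few lines of code and one more reported column. No new data are needed. The remaining limit is that a baseline-SD effect size is sensitive to restricted baseline spread. Sick leave is recorded so that "The answer is given on a 0-100 scale with 5 point increments", but entry requires "full or graded sick leave, or on work assessment allowance", which can narrow the baseline SD; hence percentage points only for that outcome. Excluding ongoing major depression may do the same for the PHQ-9, so the change in original units comes first for the questionnaires too.

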## Power analyses

In a multilevel model, the fixed effects are comparable to ordinary repeated t-tests, and thus, using this as a proxy model with a moderate effect size ( $d = 0.6$ ), power = 0.8, alpha = 0.05, tails = "two.sided", we need 25 subjects for detecting a single main effect Murayama, Usami and Sakaki (2022); see [Summary-statistics-based power analysis \(shinyapps.io\)](#). But, as stated by Van Voorhis and Morgan (2007): "*if the circumstances allow, a researcher would have better power to detect a small effect size with approximately 30 participants per variable*" (page 48). Following this rule of thumb, we plan for 30 participants per predictor (unique main effects), thus a total sample size of 300 participants. Calculating a drop-out rate of 30% gives a total sample size of  $N = 390$ . Calculating power for indirect effects – or mediation – we used the following online shiny app [Monte Carlo Power Analysis for Indirect Effects \(shinyapps.io\)](#), published by Schoemann, Boulton and Short (2023). Using (El Alaoui et al. 2015) as a proxy study for the direction and strength of association between our variables, they found that both treatment credibility and treatment adherence were significantly predictors of faster change and lower post treatment scores in a routine psychiatric care based ICBT for social anxiety disorder. In the same study, a high level of treatment credibility was associated with higher treatment adherence. Hence, defining X = treatment credibility, M = treatment adherence and Y = treatment outcomes, we set the correlation of X-M (a-path) = 0.3 ( $SD = 1$ ), X-Y (c-path) = 0.30 ( $SD = 1$ ) and M-Y (b-path) = 0.30 ( $SD = 1$ ), power = 0.8, alpha = 0.05, setting random seed to "0512", using 5000 replications with 20000 Monte Carlo draws per replication, we need  $N = 155$  to have a power of 0.80, 95% CI [0.79-0.82].

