### **Research questions**

1. To what extent does the treatment program impact Return to Work, self-reported symptoms, and everyday functioning?
2. To what extent do clinical, work-related and demographic factors affect treatment adherence and treatment response?
3. To what extent do adherence and changes in work-related self-efficacy predict outcomes?
4. What type and frequency of negative effects does participants report?
5. How do participants describe their experience of use and utility of the program, as well as its challenges and benefits?

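### The 30% drop-out allowance is miscalculated: 390 enrolled leaves 273, not the 300 it was meant to protect

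*Protocol*

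**What the plan says.** The Power analyses section of the protocol contains three sample-size statements.

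- For one main effect, using a paired t-test as a stand-in for the multilevel model with d = 0.6, two-sided alpha 0.05 and power 0.80: "we need 25 subjects for detecting a single main effect".
- For the planned sample, from a rule of thumb: "we plan for 30 participants per predictor (unique main effects), thus a total sample size of 300 participants". The next sentence adds the attrition allowance: "Calculating a drop-out rate of 30% gives a total sample size of" 390.
- For mediation, with all three correlations set at 0.30, 155 participants are said to be needed "to have a power of 0.80, 95% CI [0.79-0.82".

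The Statistical analyses section names the predictors: "The predictors are: Treatment (time), duration of sick-leave prior to treatment, treatment credibility, work related self-efficacy, depression severity and adherence". That is six. It also says that in the mixed models "data may be missing at random and at different occasions for different subjects".

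No other section gives a different drop-out rate, inflation formula or target number.

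**The concern.** The step from 300 to 390 adds 30% of the target instead of dividing by the fraction that stays. Drop-out is a share of the people enrolled, so the two operations differ, and adding a percentage of the target always gives too few. As written, 300 remaining, 30% drop-out and 390 enrolled cannot all be true.

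The sample-size paragraph is the justification on which readers of the planned papers will rely. A trial that recruits all 390 and sees exactly the attrition it predicted would still end below its own target.

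The same sentences raise a smaller question. A total of 300 at 30 per predictor implies ten predictors, but the analysis section names six. More may be intended, because the second research question asks "To what extent do clinical, work-related and demographic factors affect treatment adherence and treatment response". This is a request to make the two sections agree, not a claim that 300 is wrong.

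**Working it through.** **Inputs** (protocol, Power analyses, unless noted): target 300; drop-out 30%; stated enrolment 390; requirement for one main effect 25; requirement for mediation 155; 30 participants per predictor; six predictors named (Statistical analyses).

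**1. Reproducing the protocol's figure.** Target × (1 + rate) = 300 × 1.30 = 390. This matches exactly.

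**2. Correct allowance.** Target / (1 − rate) = 300 / 0.70 = 428.6, rounded up to 429. Check: 429 × 0.70 = 300.3, while 428 × 0.70 = 299.6. The stated figure is 429 − 390 = 39 too low for a target of 300.

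**3. What 390 delivers at 30%.** 390 × 0.70 = 273. The shortfall is 300 − 273 = 27, and 27 / 300 = 9%.

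**4. Drop-out rate at which 390 would leave 300.** 1 − 300/390 = 23.1%.

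**5. Margin over the formal requirements.** With 390 enrolled, 155 remain up to a drop-out of 1 − 155/390 = 60.3%, and 25 remain up to 1 − 25/390 = 93.6%.

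**6. Effect on power.**

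*Single main effect.* A paired t-test with d = 0.6 and two-sided alpha 0.05 has power 0.82 at n = 25 (0.80 at n = 24), so the protocol's 25 is sound. The smallest effect detectable with 80% power, approximately (1.96 + 0.84)/√n, is:

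| n | detectable d |
|---|---|
| 300 | 0.162 |
| 273 | 0.170 |

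*Mediation.* A simulation with all correlations at 0.30 and Monte Carlo confidence intervals for the indirect effect (6000 replicates, 2000 draws each) gave:

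| n | power |
|---|---|
| 155 | 0.804 |
| 273 | 0.970 |
| 300 | 0.983 |

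The value at 155 agrees with the protocol's 0.80.

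**7. Predictors.** 300 / 30 = 10 implied, against six named. With 273 remaining, ten predictors have 273 / 10 = 27.3 participants each, and six have 273 / 6 = 45.5 each.

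**The case against.** The arithmetic itself is not in dispute. The best case on the other side concerns what it means.

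- **The protocol never says that 300 is the number to remain.** It calls both 300 and 390 a total sample size. That is true, and the reading is an inference. But an attrition allowance on top of 300 has no purpose unless 300 is what should be left.
- **The number remaining is not the number analysed.** Baseline questionnaires are mandatory before the first module, and the mixed models use whatever occasions a participant provides. This stands. The detectable effects above treat drop-outs as contributing nothing, so they overstate the loss. The number remaining matters more for mediation, which needs the mediator during treatment and the outcome afterwards, and there power is about 0.97.
- **The target is a soft rule of thumb.** Its source, as the protocol quotes it, is approximate and conditional on circumstances. At ten predictors, 27.3 each is close to 30; at the six named, 45.5 each is well above it. This also stands, and it limits the consequence. It does not make the inflation step correct.
- **A longer predictor list may sit in an analysis plan that is not shown.** That is possible, and it is why the predictor count is raised only as something to reconcile.
- **Keeping 390 on the ground that 273 exceeds 25 and 155 leaves 390 without a derivation.** This is fair. The corrected text should therefore say openly that 273 falls below 300.

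**Conclusion.** The concern holds, as a minor error. At the stated 30% drop-out, 390 enrolled leaves 273, which is 27 (9%) below 300. Leaving 300 would take 429 enrolled, or drop-out of no more than 23.1%. No formal power statement fails, because 273 exceeds both 25 and 155 by a wide margin.

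This rests on two readings: that 300 is the number meant to be left after attrition, and that 30% is a share of those enrolled. Both are the ordinary meanings, and nothing in the protocol suggests others.

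**What to change.** Correct the sentence in the Power analyses section. The least costly wording keeps both the enrolment and the drop-out assumption, for example: *With 390 enrolled and 30% drop-out, about 273 participants are expected to remain. This is below the planning figure of 300 but above the 25 and 155 required by the power calculations.*

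If the sponsor wants 300 to remain, there are two consistent alternatives:

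- plan for 429 at 30% drop-out, which is 39 more participants; or
- keep 390 and justify a drop-out rate of at most 23%. The protocol offers no support for such a rate at present, so evidence would be needed.

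In the same edit, make the predictor count agree with the Statistical analyses section. If ten are meant, name them and say that 273 gives about 27 each, slightly under the planned 30. If six are meant, explain how 300 was reached.

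Under the recommended wording the cost is one or two sentences. Recruitment, the drop-out assumption and the stated power do not change.
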